Aim 4 (secondary outcome): Theta oscillations in frontal cortex are hypothesized to play a causal role in precision of working memory representations. During the probe, the participant responds with a specific color from a comprehensive color wheel. Plus or minus 15 degrees around the color wheel is considered "correct." For the correct trials, the precision is calculated as the distance in degrees from the response of the participant to the actual color of the memory item. To investigate if theta oscillations play a causal role in precision, the impact of theta stimulation on precision relative to arrhythmic and as a function of visual field will be investigated.

Aim 5 (secondary outcome): Stimulation that is aligned to the endogenous activity of the brain is hypothesized to entrain neural activity. Inter-trial phase coherence (ITPC) quantifies alignment of neural oscillations across trials. Stimulation in frontal-theta and parietal-alpha is proposed to increase ITPC in a frequency specific manner relative to control stimulation.

*Phase Two Overarching Goal:* Investigate the causal role of in-phase theta-frequency between frontal and parietal cortex in the prioritization and suppression of working memory representations.

Aim 6 (primary outcome): Stimulation that is delivered in-phase to frontal and parietal cortex in the theta frequency is hypothesized to increased working memory capacity relative to anti-phase theta stimulation. Working memory capacity is quantified using Pashler's metric.

Aim 7 (primary outcome): Stimulation that is delivered in-phase to frontal and parietal cortex in theta frequency is hypothesized to increase functional connectivity between the regions in a frequency specific manner. Functional connectivity will be measured using weighted phase lag index. In addition, we hypothesize that in-phase theta frequency stimulation will increase WPLI magnitude for retro-cues to the right visual field greater than the increase for stimulation with a retro-cue to the left visual field. This hypothesis is motivated by the finding that the left hemisphere processes information for the contralateral visual hemifield and that theta oscillations are linked to the active processing of information.

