forms of arrhythmic stimulation are used: arrhythmic-in-synchrony stimulation delivers simultaneous stimulation to the two sites, but there is no consistent frequency component to the stimulation. Thus, activity in the two sites may be synchronized but not in a frequency-specific manner. The second control condition for stimulation is arrhythmic-independent where two trains of TMS are delivered in random patterns. There is no synchronization between the two pulse trains. Arrhythmic-independent controls for frequency and synchrony specificity of stimulation. All analyses will be performed on the difference from condition-matched arrhythmic TMS (in-phase minus arrhythmic-in-synchrony and anti-phase minus arrhythmic-independent). The key analyses are built upon a three-way design: with factors TMS frequency (theta and alpha), TMS alignment (in-phase and anti-phase), and cue direction (left and right retro-cue).

**Aim 6 (primary outcome):** Stimulation that is delivered in-phase to frontal and parietal cortex in the theta frequency is hypothesized to increased working memory capacity relative to anti-phase theta stimulation. Working memory capacity is quantified using Pashler's metric (see Aim 1). We will perform a two-way repeated-measures ANOVA with a between participants factor of TMS frequency (theta and alpha) and within-participants factor of TMS alignment (in-phase and anti-phase). We hypothesize to find a significant interaction ( $p < 0.05$ ) between TMS frequency and TMS alignment such that in-phase TMS in theta-frequency increases working memory capacity. Post-hoc t-tests will be performed using Tukey's method to control for multiple comparisons. *Sensitivity analysis:* Similar to aim 1, the impact of stimulation on hit rate, false alarm rate, and overall accuracy will be calculated. The robustness of these effects will be estimated using an individual differences analyses where baseline performance is used as a covariate to improve model estimation. Finally, the titration of working memory load by participant will be added as a covariate to explore if this factor changes the model estimation. These are framed as exploratory analyses.

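### In phase two the two alignments are measured against different controls, so every planned alignment effect is in-phase versus anti-phase minus a difference between controls that the plan never estimates

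*Combined protocol and SAP*

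**What the plan says.** Section 11.1 introduces phase two with a rule covering all of its analyses: "All analyses will be performed on the difference from condition-matched arrhythmic TMS (in-phase minus arrhythmic-in-synchrony and anti-phase minus arrhythmic-independent". It describes the two controls as follows.

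- For the control paired with in-phase: "arrhythmic-in-synchrony stimulation delivers simultaneous stimulation to the two sites, but there is no consistent frequency component to the stimulation". It adds: "Thus, activity in the two sites may be synchronized but not in a frequency-specific manner".
- For the control paired with anti-phase: "There is no synchronization between the two pulse trains". Its purpose is given as "Arrhythmic-independent controls for frequency and synchrony specificity of stimulation".

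The Aim 6 hypothesis (primary) is that in-phase theta stimulation "is hypothesized to increased working memory capacity relative to anti-phase theta stimulation". The model is given as "We will perform a two-way repeated-measures ANOVA with a between participants factor of TMS frequency (theta and alpha) and within-participants factor of TMS alignment", the test is the interaction at 0.05, and Tukey-adjusted post-hoc t-tests follow. Aim 8 (secondary) tests a main effect of alignment on phase lag and expects the effect to be strongest for theta.

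The plan has no contrast between the two controls and no analysis of in-phase against anti-phase without the subtraction. The Aim 6 sensitivity analyses change the outcome measure or add covariates; they do not alter the subtraction rule.

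**The concern.** Each control removes something different. Arrhythmic-in-synchrony shares simultaneous delivery with in-phase, so subtracting it takes out any effect of synchrony that does not depend on rhythm. Arrhythmic-independent has no fixed relation between sites, so subtracting it leaves the whole effect of a fixed offset in the anti-phase score. The difference between the two scores therefore contains a comparison of the controls that the Aim 6 hypothesis does not mention.

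What is at stake is the sentence the trial can write at the end. A theta post-hoc result or an Aim 8 alignment effect could arise wholly from the controls while in-phase and anti-phase give the same result. It could also be null because the controls offset a real difference. As planned, the reader could not tell these cases apart. Separately, subtracting two further noisy scores may cost power.

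**Working it through.** **Inputs.** From the documents: the subtraction rule and the Aim 6 model (Section 11.1); 48 completers per phase (Section 3); theta or alpha assigned between participants in phase two (Section 4.1); inter-pulse intervals of about 100 ms for alpha and 200 ms for theta, five pulses per train (Section 6.2). Assumed, because the documents give no value: an even 24:24 split, and the variances and correlations of the four scores.

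**The plan's own figure.** Section 11.2 gives no calculation for an alignment contrast. Its N of 48 is for the phase one site-by-frequency interaction. It reproduces as a one-sample (paired) two-sided t-test at 0.05 with effect size 0.532: power at 48 is 0.9505. It says nothing about the precision of the phase two contrast.

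**1. What is estimated.** (I − S) − (A − N) = (I − A) − (S − N). This equals I − A only if S = N on average.

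**2. Where S − N goes.** Let g be S − N in an arm.

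| Test | Contribution of the control gap |
|---|---|
| Theta post-hoc, in-phase v anti-phase | −g(theta), in full |
| Aim 8 main effect of alignment | −average of g over the two arms |
| Aim 6 frequency-by-alignment interaction | −[g(theta) − g(alpha)]; zero if the gaps are equal |

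**3. Illustration of the bias.** Suppose I = A exactly and g = 0.5 within-condition SD (an assumed value). With equal correlation ρ among conditions, the SD of the double difference is √[4(1 − ρ)]: 2.00 at ρ = 0 and 1.41 at ρ = 0.5. Rejection rates from the noncentral t, nominal 5%:

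| | ρ = 0 | ρ = 0.5 |
|---|---|---|
| Theta-only test, n = 24 | 22% | 38% |
| Interaction, 24 v 24, gap in theta arm only | 14% | 22% |
| Interaction, same gap in both arms | 5% | 5% |

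The theta-only row is an unadjusted t-test; the Tukey adjustment would change the rate but not the bias.

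**4. Could the gap differ by arm?** A five-pulse train spans four intervals: about 4 × 200 = 800 ms for theta and 4 × 100 = 400 ms for alpha. Section 2.2 matches arrhythmic trains to the length of the rhythmic train when it describes arrhythmic-theta and arrhythmic-alpha. If phase two does the same, two independent random trains overlap differently in the two arms. Equality is therefore not assured, though nothing shows that it fails.

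**5. Precision.** With common SD σ and equal correlation ρ:

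- Var(I − A) = 2σ²(1 − ρ)
- Var[(I − S) − (A − N)] = 4σ²(1 − ρ)

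The ratio is 2 and the standard error is √2 = 1.41 times larger. Now let each rhythmic condition correlate ρm with its own control and ρc with the other, keeping ρ for I with A and S with N. The ratio becomes 2 − 2(ρm − ρc)/(1 − ρ):

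| ρm − ρc | −0.1 | 0 | 0.1 | 0.2 |
|---|---|---|---|---|
| ρ = 0.5 | 2.4 | 2.0 | 1.6 | 1.2 |
| ρ = 0.7 | 2.67 | 2.0 | 1.33 | 0.67 |

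Binomial trial noise in percent correct alone gives 2.00 to 2.10 for accuracies from 60% to 85%.

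**6. Cost in power if the ratio is 2.** An effect of 1.0 SD on the direct contrast, compared 24 v 24, has power 0.92. On the double difference the standardised effect is 1.0/1.41 = 0.71 and power is 0.67.

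**The case against.** The pairing is deliberate and has a rationale. In-phase and its control pulse both sites together; anti-phase and its control pulse them separately. Removing synchrony that is not frequency-specific suits a hypothesis about theta connectivity. The stated test is the interaction, from which a common gap drops out. All of this stands.

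The unsubtracted contrast is not clean either. Anti-phase gives up to ten separate clicks per train against five for in-phase. With a 180-degree offset, the clicks come about every 100 ms for theta and every 50 ms for alpha, so this sensory difference varies by frequency and need not cancel in the interaction. The protocol takes sound seriously: Section 5.2 plays white noise for that reason. The planned controls match separate delivery, though not click rate.

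Three stronger readings are tempting, and the documents support none of them.

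- A reader might infer that the primary interaction is invalid. It is biased only if S − N differs between arms, and the documents give no evidence of any gap in memory capacity. Their remark about possible synchronisation concerns neural activity.
- A reader might infer that the variance is doubled outright. That needs equal variances and correlations. Strong correlation with the matched control would shrink the penalty or reverse it.
- A reader might infer that the direct contrast should replace the primary outcome variable, with success tied to a theta-only interval excluding zero. Given the click-rate difference, that exchanges one possible bias for another and adds a criterion resting on one arm.

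What the objection does not answer is that the hypothesis is worded as I − A, the test estimates something else, and S − N goes unreported. Section 4 intermixes the stimulation types within every block, so participant and session level already cancel in I − A.

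**Conclusion.** The concern holds as a mismatch between the comparison Aim 6 states and the one Section 11.1 tests. The algebra is exact and needs no assumption. Any non-zero S − N passes in full into the theta post-hoc comparison and, averaged over arms, into the Aim 8 alignment main effect. It reaches the primary interaction only through a difference between arms. The rejection rates above depend on an assumed gap of 0.5 SD and show scale only.

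The precision cost is about a doubling of variance under equal variances and correlations, and 1.2 to 2.4 times for the departures examined around a correlation of 0.5. It is wider, and can reverse, at higher correlations. Unlike a common gap, extra variance does not cancel in the interaction. This is an inexpensive improvement that changes what Aims 6 and 8 can conclude; it is no reason to discard the planned analysis.

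**What to change.** In Section 11.1, for phase two:

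1. Keep the control-subtracted frequency-by-alignment interaction as planned, and state that its alignment effect estimates (I − A) − (S − N).
2. For Aims 6 and 8, pre-specify the same frequency-by-alignment analysis on the unsubtracted in-phase and anti-phase scores. Report the theta I − A estimate with its confidence interval.
3. Report S − N with its interval in each frequency arm.
4. Conclude that in-phase theta exceeds anti-phase theta only where the direct contrast agrees in direction and the subtracted effect is not explained by S − N.

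The cost is a little more analysis on data already collected for the planned tests. The drawback is that the direct contrast does not control for the larger number of separate audible pulses in anti-phase, which also varies by frequency, so neither contrast should be read alone. The protocol is at version 7.0, dated September 2025, and does not say whether phase two results have been examined. The addition should be dated, and described as pre-specified only if they have not.

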## 6.2 SPECIAL ASSAYS OR PROCEDURES

Each participant will receive stimulation in the fourth and fifth sessions, separated by about one week. Motor thresholding will take place in the first stimulation session. For stimulation day, the rhythmic TMS trains are delivered on every trial of the task (there are 600 trials per session). Each train of TMS consists of 5 pulses. There will be a total of 3000 pulses delivered per session in phase one, and with two coils there will be total of 6000 pulses per session in phase two. Each TMS train will be separated by a minimum of 5 seconds. There are three possible trains: individual alpha frequency with an approximate 100 milliseconds inter-pulse interval, individual theta frequency with a 200 milliseconds inter-pulse interval, and arrhythmic with a variable inter-pulse interval (with a minimum of 20 milliseconds inter-pulse interval). The inter-pulse interval, inter-train interval, number of trains, and TMS intensity are all under the safety guidelines set forth by Rossi et al. 2009 and is typical for experiments that deliver online TMS (Hanslmayr et al. 2014; Albouy et al. 2017).

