**Aim 5 (secondary outcome):** Stimulation that is aligned to the endogenous activity of the brain is hypothesized to entrain neural activity. Inter-trial phase coherence (ITPC) quantifies alignment of neural oscillations across trials. Stimulation in frontal-theta and parietal-alpha is proposed to increase ITPC in a frequency specific manner relative to control stimulation. A similar method for extracting instantaneous phase is used as that used to extract instantaneous amplitude (Aim 2). ITPC is calculated as the average phase angle in complex space of unit vectors across trials, then taking the magnitude of the resulting vector. These ITPC values are then averaged for the second half of the TMS train as described in (Aim 2). Frontal-theta and parietal-alpha ITPC values will be submitted to a two-way repeated-measures ANOVA with TMS frequency by TMS site. We hypothesize to find a significant interaction ( $p < 0.05$ ) between TMS site and TMS frequency such that theta ITPC in frontal cortex increases greater for TMS to frontal in theta frequency and alpha ITPC in parietal cortex increases greater for TMS to parietal cortex in alpha frequency. Post-hoc t-tests will be performed using Tukey's method to control for multiple comparisons. *Sensitivity analysis:* Similar to the sensitivity analysis of Aim 2, the time-course and topographic plots with cluster analysis will quantify the spread of these effects.

**Phase Two Overarching Goal:** Investigate the causal role of in-phase theta-frequency between frontal and parietal cortex in the prioritization and suppression of working memory representations. To control for non-specific effects of dual-site rhythmic TMS, we will use an active control: arrhythmic TMS (randomized inter-pulse-interval). Two

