**Aim 7 (primary outcome):** Stimulation that is delivered in-phase to frontal and parietal cortex in theta frequency is hypothesized to increase functional connectivity between the regions in a frequency specific manner. Functional connectivity will be measured using weighted phase lag index (WPLI). To calculate WPLI, first Morlet wavelet convolution is performed to extract instantaneous phase and amplitude for the frequency of interest for the two target sites. Next, the cross-spectral density is calculated (one signal multiplied by the complex conjugate of the other). From the cross-spectral density the imaginary component of the resulting signal is extracted. Then those imaginary values are averaged over the time frame of instance (here, the second half of the stimulation train). Finally, the magnitude of the resulting vector is taken to be the WPLI. This metric quantifies the consistency of phase lag between the two target regions and is weighted towards signals with a 90 or 270 degree offset to address a common confound in EEG, volume conduction. We hypothesize that in-phase theta-frequency stimulation will increase theta-frequency WPLI strength between frontal and parietal cortex. In addition, we hypothesize that in-phase theta frequency stimulation will increase WPLI magnitude for retro-cues to the right visual field greater than the increase for stimulation with a retro-cue to the left visual field. This hypothesis is motivated by the finding that the left hemisphere processes information for the contralateral visual hemifield and that theta oscillations are linked to the active processing of information. Using a two-way ANOVA with factors for TMS frequency (theta or alpha) and retro-cue direction (left or right), we hypothesize a significant interaction ( $p < 0.05$ ) between TMS frequency and retro-cue direction such that WPLI magnitude is the greatest for theta-frequency stimulation with a retro-cue to the right visual field. Post-hoc t-tests will be performed using Tukey's method to control for multiple comparisons. *Sensitivity analysis:* The frequency, topographic, and spatial specificity of these effects will be explored. Similar to Aim 2, the time-course of WPLI can be estimated using a sliding window to demonstrate if functional connectivity rises and peaks at the end of the stimulation train. Furthermore, the topographic increase in functional connectivity will be quantified across the scalp to see if the effect is specific to the targeted regions. Finally, the frequency specificity will be explored by calculating functional connectivity across the full spectral range (2-30 Hz) and the specificity of connectivity changes in frequency domain will be displayed. Together, these analyses will establish the robustness

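### The Aim 7 WPLI recipe averages only over about two cycles and never states averaging across trials; followed within each trial, it does not measure how stable the phase lag is

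*Combined protocol and SAP*

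**What the plan says.** Section 11.1, Aim 7 (primary outcome) sets out the index step by step: Morlet wavelet convolution at the two target sites, cross-spectral density, imaginary part, then "Then those imaginary values are averaged over the time frame of instance (here, the second half of the stimulation train". It ends: "Finally, the magnitude of the resulting vector is taken to be the WPLI". No divisor and no wavelet width are given, and trials are not mentioned. The stated purpose is: "This metric quantifies the consistency of phase lag between the two target regions".

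Three other places bear on the reading:

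- **Aim 7, sensitivity analysis:** "the time-course of WPLI can be estimated using a sliding window".
- **Aim 5 (ITPC):** "ITPC is calculated as the average phase angle in complex space of unit vectors across trials". Only afterwards are those values averaged over the second half of the train.
- **Section 6.2 (timing):** "Each train of TMS consists of 5 pulses", with "individual theta frequency with a 200 milliseconds inter-pulse interval" and "individual alpha frequency with an approximate 100 milliseconds inter-pulse interval".

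The phase two overview in section 11.1 has every measure analysed as a difference from matched arrhythmic stimulation.

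**The concern.** An index of lag stability must average over something across which the lag could vary. If the only averaging is over time within a trial, the question becomes whether the lag drifts during the window. Two signals filtered at the same frequency often drift little over two cycles even when they are unrelated. Signed values then seldom cancel, and the magnitude is large whether or not the sites are coupled. Averaging across trials is different: uncoupled sites have a different lag on each trial, so their signed values cancel.

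A programmer who follows Aim 7 literally would average within trial. A primary outcome would then lose most of its ability to detect moderate coupling. As the text gives no denominator, the value would also rise with signal amplitude, which rhythmic stimulation is itself expected to raise (Aim 2).

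**Working it through.** The documents give no numerical WPLI, so there is no figure of the plan's own to reproduce.

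**Window.** Five pulses span 4 intervals (section 6.2).
- Theta: 4 x 200 ms = 800 ms; second half 400 ms; 400 / 200 = 2 cycles.
- Alpha: 4 x 100 ms = 400 ms; second half 200 ms; 200 / 100 = 2 cycles.

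**Candidate readings.** Let I(k,t) be the imaginary cross-spectrum on trial k at time t in the window.
- A, within trial, normalised: |mean over t of I| / mean over t of |I|, then averaged over trials.
- B, within trial, literal text: |mean over t of I|, then averaged over trials.
- C, across trials, normalised: |mean over k of I| / mean over k of |I| at each t, then averaged over t.
- D, pooled, normalised: |mean over k and t of I| / mean over k and t of |I|.

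**Assumptions not in the documents.** Independent pink-noise signals at 250 Hz; no TMS artefact or volume conduction; wavelets of 3, 5 and 7 cycles; 20 to 30 replicates. Both 75 and 150 trials were run (the two per-condition counts in section 4.1).

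**Uncoupled sites, 5 Hz**

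| Reading | 3 cycles | 5 cycles | 7 cycles |
|---|---|---|---|
| A, mean | 0.66 | 0.76 | 0.82 |
| A, median trial | 0.75 | 0.92 | 0.995 |

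C gives 0.09 to 0.12 and D gives 0.06 to 0.09. Across 4, 5, 7 and 10 Hz, A stays at 0.65 to 0.83 and C at 0.06 to 0.15.

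The level of A depends on the assumed signal. White noise gives 0.66 / 0.77 / 0.82. Narrowband signals give 0.80 / 0.82 / 0.84 (SD 1 Hz) or 0.88 / 0.89 / 0.89 (SD 0.5 Hz). Pink noise with a ratio of means in place of a mean of trial ratios gives 0.72 / 0.84 / 0.89.

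**Response to coupling (5 Hz, 5 cycles, 75 trials, 90-degree lag)**

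| Shared variance | A | B (arbitrary units) | C |
|---|---|---|---|
| 0 | 0.77 | 6.2 | 0.14 |
| 0.1 | 0.77 | 6.2 | 0.21 |
| 0.3 | 0.79 | 7.0 | 0.55 |
| 0.5 | 0.83 | 8.3 | 0.79 |
| 0.7 | 0.89 | 10.4 | 0.94 |
| 0.9 | 0.97 | 13.1 | 0.99 |

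If the arrhythmic control were uncoupled, the analysed difference at 0.3 shared variance would be 0.79 - 0.77 = 0.02 for A, against 0.55 - 0.14 = 0.41 for C. At a 60-degree lag (150 trials), A moves from 0.77 to 0.78 and C from 0.10 to 0.50.

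**Amplitude.** With no coupling, doubling the amplitude product doubles B: 5.9 to 11.8.

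**Ranking under B.** This uses a separate run (5 cycles, 150 trials, its own arbitrary units). Uncoupled sites give 42. Shared variance of 0.9 gives 84 at a 60-degree lag, 33 at 20 degrees and 20 at 10 degrees. The last two lie below uncoupled: 33 / 42 = 0.79 and 20 / 42 = 0.48. The cause is that the shared imaginary part scales with the sine of the lag: 84 / 0.866 = 97; 97 x 0.342 = 33; 97 x 0.174 = 17, with noise lifting the last to 20. Averaged across trials, still without a denominator, the values are 33 and 17 against 4.5 for uncoupled sites, so the order is restored.

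**Trial count.** Over the twelve uncoupled settings (four frequencies, three widths), C averages 0.119 with 75 trials and 0.094 with 150.

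**The case against.** The strongest reply is that the text leaves averaging across trials unstated and does not rule it out. If signed values are pooled over trials and window before the magnitude is taken, uncoupled sites score about 0.1 or less and the problem disappears. The stated purpose of the index fits that reading. A sliding window can also be run on trial-pooled data, and the contrast with Aim 5 may show only uneven detail. This stands: a reader might infer that the plan has chosen time in place of trials, and the documents do not establish that. What remains is that time is the only averaging dimension the recipe names.

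A reader might also infer that the index sits at an upper limit for uncoupled sites. The documents do not support that either. The formula as written has no denominator and so no upper limit. Once normalised within trial, the uncoupled mean depends on unstated wavelet width and signal bandwidth.

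Finally, every analysis subtracts the arrhythmic condition, so a null level common to both conditions cancels. That also stands, and it means a high baseline alone should not be read as false connectivity. It does not answer the loss of sensitivity (0.02 against 0.41 above), the dependence on amplitude where rhythmic and arrhythmic trains differ in power, or a reversed ranking.

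**Conclusion.** The concern holds as a fault in the stated rule for a primary outcome. Followed as written, within trial, the Aim 7 index does not measure what it is said to measure. Under assumed pink noise and 3- to 7-cycle wavelets, uncoupled sites score about 0.65 to 0.8 after normalisation, and up to about 0.9 under other assumed bandwidths or ratio definitions, against about 0.1 across trials. Adding the denominator alone does not cure this, since those values already include it.

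The literal formula has two further weaknesses: it scales with amplitude, and it can place strong coupling at a small lag below no coupling. The second matters because Aim 8 expects in-phase stimulation to shorten the lag.

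The sizes rest on simulated signals, not on trial data. The two-cycle window and the absence of any stated averaging across trials come straight from the documents. Whether the analysis script shares the fault cannot be told from them.

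**What to change.** Replace the averaging step in Aim 7 with the full WPLI formula:

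- Average signed imaginary values across the trials of a condition before any magnitude is taken. Either do this at each time point and then average the index over the second half of the train, or pool over trials and window together. State which.
- Divide by the mean absolute imaginary value over the same set.
- Use the same order for the sliding-window time course.
- State the wavelet width.
- Use equal trial numbers for the rhythmic and arrhythmic conditions, because the null value of the index falls as trials are added.

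The cost is one rewritten sentence in section 11.1 and, if the script averages within trial, a change in its order of averaging. If the script already averages across trials, only the text changes. No new data are needed.
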